6.5.2.6. Concomitant Medication

Medications will be coded using the GSKDRUG dictionary.

The frequencies and percentages of subjects starting/reporting concomitant medications during all study period will be tabulated by vaccine group.

7. ANALYSIS INTERPRETATION

All analyses will be descriptive.

8. CONDUCT OF ANALYSES

8.1. Sequence of analyses

Not applicable for this study.

8.2. Statistical considerations for interim analyses

No interim analysis of data from this study is planned.

9. CHANGES FROM PLANNED ANALYSES

Not Applicable.

10. LIST OF FINAL REPORT TABLES, LISTINGS AND FIGURES

The TFL TOC provides the list of tables/listings and figures needed for the study report.

The mock tables referred under column named 'layout' can be found in legacy-NV/GSK SDD dedicated folder for standard tables and in **Annex 3** for study specific mock table/figure/listing. The latter table/figure/listing are identified by the prefix SS_ in the TFL Toc.

11. ANNEX 1 STANDARD DATA DERIVATION RULE AND STATISTICAL METHODS

11.1. Statistical Method References

The exact two-sided 95% CIs for a proportion within a group will be the Clopper-Pearson exact CI [Clopper CJ, Pearson ES. The use of confidence or fiducial limits illustrated in the case of binomial. *Biometrika*. 1934;26:404-413].

11.2. Standard data derivation

NV legacy

The incomplete date derivations are as follow for an event with start and stop date:

For an incomplete start date, if the day is missing while the month and year are available:

- when the month and year are identical to a complete stop date then the start date is imputed to the stop date.
- when the month and year are not identical to a complete stop date then the start day is imputed to the first day of the month.

For an incomplete start date, if the day and month are missing while the year is available:

- when the year is identical to a complete stop date then the start date is imputed to the stop date.
- when the year is not identical to a complete stop date then the start day/month is imputed to 01Jan.

For an incomplete stop date, if the day is missing while the month and year are available:

- when the month and year are identical to a complete start date then the stop date is imputed to the start date.
- when the month and year are not identical to a complete start date then the stop day is imputed to the first day of the month.

For an incomplete stop date, if the day and month are missing while the year is available:

- when the year is identical to a complete start date then the stop date is imputed to the start date.
- when the year is not identical to a complete start date then the start day/month is imputed to 31dec.

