8.4.2.1.3 Analysis of Unsolicited Adverse Events

This analysis applies to all adverse events occurring during the study, judged either as probably related, possibly related, or not related to vaccination by the investigator, recorded in AE CRF, with a start date on or after the date of vaccination. AE starting prior to the vaccination will only be listed. The original verbatim terms used by investigators to identify adverse events in the CRFs will be mapped to preferred terms using the MedDRA dictionary. The adverse events will then be grouped by MedDRA preferred terms into frequency tables according to system organ class.

All reported adverse events, as well as adverse events judged by the investigator as at least possibly related to study vaccine, will be summarized according to system organ class and preferred term within system organ class. These summaries will be presented by vaccination group and by interval of study observation. When an adverse event occurs more than once for a subject, the maximal severity and strongest relationship to the vaccine group will be counted.

Separate summaries will be produced for the following categories:

- Serious adverse events
- Adverse events that are possibly or probably related to vaccine

- Adverse events of special interest
- New onset of chronic disease
- Potential immune-mediated diseases (pIMDs) adverse event leading to withdrawal • Adverse events leading to a medically attended visit
- Adverse event by data source.

Data listings of all adverse events will be provided by subject. In addition, adverse events in the categories above will be provided as listed data.

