6. STATISTICAL ANALYSES

Note that standard data derivation rule and stat methods are described in **Annex 1** and will not be repeated below.

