6.5.2.3. Unsolicited Adverse Events

All the unsolicited adverse events occurring during the study, judged either as probably related, possibly related, or not related to vaccination by the investigator, will be recorded. The original verbatim terms used by investigators to identify adverse events in the CRFs will be mapped to preferred terms using the MedDRA dictionary. The unsolicited adverse events will then be grouped by MedDRA preferred terms into frequency tables according to system organ class. Adverse events judged by the investigator as at least possibly related to study vaccine will be summarized by vaccine group, according to system organ class and preferred term within system organ class. When an unsolicited adverse event occurs more than once for a subject, the maximal severity and strongest relationship to the vaccine group will be counted.

Only vaccine-emergent adverse events (see **section 7.1** of protocol for definition) will be analyzed, i.e., excluding those after a subject has given informed consent but before vaccination.

The summaries will be presented for all study period and will include frequency distributions of the different adverse events:

- Onset between day 1 and study termination (all study period).

The analysis of unsolicited adverse events comprises the following categories:

- Any unsolicited adverse event.
- Possibly or probably related unsolicited adverse events.
- Unsolicited adverse events leading to death.
- Serious adverse events.
- Possibly or probably related serious adverse event.
- Unsolicited adverse events leading to premature withdrawal from study.
- Unsolicited adverse events leading to hospitalization.
- Unsolicited adverse events of special interest.

- Solicited adverse events continuing beyond day 7 will be coded by MedDRA and combined with the respective unsolicited adverse events.

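### The SAP 11.2 rule for incomplete dates can place a post-vaccination unsolicited AE before vaccination and so drop it from the AE tables

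*SAP*

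**What the plan says.** SAP section 6 notes that "standard data derivation rule and stat methods are described in" Annex 1, so SAP 11.2 governs the safety analyses. Its start-date rules are:

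- **Day missing.** If a complete stop date falls in the same month and year, the start is set to that stop date. Otherwise, if "month and year are not identical to a complete stop date then the start day is imputed to the first day of the month".
- **Day and month missing.** A complete stop date in the same year is used; "when the year is not identical to a complete stop date then the start day/month is imputed to 01Jan".

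For a stop date with the day missing, when month and year are "not identical to a complete start date then the stop day is imputed to the first day of the month".

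The scope is introduced thus: "The incomplete date derivations are as follow for an event with start and stop date". Nothing is said about ongoing AEs, and no line mentions vaccination or Day 1.

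Two passages then filter AEs on timing. SAP 6.5.2.3 analyses only vaccine-emergent AEs, "excluding those after a subject has given informed consent but before vaccination", and summarises onset from Day 1. Protocol Version 2, 8.4.2.1.3, covers AEs "with a start date on or after the date of vaccination" and adds: "AE starting prior to the vaccination will only be listed".

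**The concern.** The imputation rule and the filter do not fit together. Imputing to the 1st of the month takes the earliest possible date, while the filter removes anything earlier than vaccination. An AE known to have started in the vaccination month, but not on which day, can therefore be moved ahead of the injection by the imputation alone.

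The tables at stake are those for unsolicited AEs, including the secondary endpoint on the number of subjects with such events. Among true post-vaccination AEs the error can only remove events. When the stop date is complete, the AEs at risk are those that cross a month end, so longer AEs are lost more often than short ones.

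**Working it through.** The plan gives no figure to reproduce, so the check applies the rule literally.

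**Worked example.** Vaccination 15 March, true onset 20 March, start recorded with the day missing.

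- Stop 2 April: imputed start 1 March, 14 days before vaccination. The AE is listed only.
- Stop 25 March: imputed start 25 March. The AE is kept.
- Onset in April instead, stop in May: imputed start 1 April. The AE is kept.

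The fault thus needs onset in the calendar month of vaccination, no complete stop date in that month, and vaccination on a day other than the 1st (353 of 365 dates).

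**Enumeration: assumptions.** All 365 vaccination dates in 2017; onset on each of days 0-28 after vaccination, equally weighted (general AE collection runs to Visit 4, Day 29, under Protocol 7.1); start day missing; complete stop date L days after onset. Total cases: 365 × 29 = 10,585.

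**Formula.** For vaccination on day v ≥ 2 of a month with M days, the misdated onset days s satisfy max(v, M − L + 1) ≤ s ≤ min(M, v + 28). For v = 1 there are none. If the stop day is also missing, the lower bound is simply v. Counts are summed over v within each month; 2017 has seven 31-day months, four 30-day months and a 28-day February.

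| Stop date | Per 31-day month | Per 30-day month | February | Total | Share of 10,585 |
|---|---|---|---|---|---|
| L = 1 | 29 | 29 | 27 | 346 | 3.3% |
| L = 3 | 86 | 84 | 78 | 1,016 | 9.6% |
| L = 7 | 188 | 182 | 168 | 2,212 | 20.9% |
| L = 14 | 328 | 315 | 287 | 3,843 | 36.3% |
| L = 28 | 461 | 434 | 378 | 5,341 | 50.5% |
| Stop day missing too | 464 | 435 | 378 | 5,366 | 50.7% |

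For example, at L = 14: 7 × 328 + 4 × 315 + 287 = 3,843.

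**Sensitivity to the vaccination date.** The share is 0% for vaccination on the 1st. The maximum for any single date is 3%, 10%, 24%, 48% and 97% for L = 1, 3, 7, 14 and 28. At L = 14 it is 48% on the 15th and 12% on the 28th. With both days missing it is 91% on the 5th, 57% on the 15th and 12% on the 28th. Restricting vaccination to 8 February to 20 November 2017 (an assumption taken from the dates in SAP section 1) gives 3%, 10%, 21%, 37% and 51%, and 51% with both days missing.

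**Sensitivity to the onset window.** Over days 0-84 there are 365 × 85 = 31,025 cases. The shares are 1.1%, 3.3%, 7.2%, 12.4% and 17.2%, and 17.3% (5,373) with both days missing.

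**The case against.** The strongest objection is that the SAP never says an imputed date decides whether an AE is vaccine-emergent. SAP 6.5.2.3 refers to Protocol 7.1 for the definition, and that section defines emergence by when the event actually occurred. On that view this is a request for clarification. It stands in part: the link is an inference. But when the day is missing, actual timing within the vaccination month cannot be read from the date field, and SAP 11.2 is the only stated way to supply it. If some other source was intended, the SAP should name it.

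Second, few AEs may be affected, possibly none. AEs are collected by interview at Days 8, 15 and 29, and the sponsor can query dates. Diary-based solicited tables and laboratory shift tables are untouched. SAEs, reported within 24 hours, and neutropenia, tied to a dated blood count, are unlikely to be affected. All of this stands. It limits the importance of the point but does not make the rule right.

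Third, the endpoint spans 84 days, over which the shares are roughly a third of those for days 0-28. That is correct. The shorter window was used because general AE collection stops at Visit 4; both are shown.

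Fourth, the branch leading to the 1st of the month could be read as requiring a complete stop date in another month. The both-days-missing share would then not arise, because no rule would exist for that case. This ambiguity is real, and it is a further reason to rewrite the text.

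Finally, a vaccination-date floor counts some pre-vaccination AEs as emergent. That is true, and the size is given with the fix.

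**Conclusion.** The concern holds, at low severity. Followed literally, SAP 11.2 dates some true post-vaccination AEs before vaccination, and nothing elsewhere in the protocol or SAP corrects this. Year-only start dates have the same defect.

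The shares apply only to AEs with a missing start day. They rest on uniform onset over the stated window and an even spread of vaccination dates. How many AEs have a missing start day is unknown. That they leave the tables depends on the imputed date setting the emergent flag, which is the natural reading but is not stated.

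With up to 50 subjects, one lost event can change a table row. Against that, the endpoint counts subjects, so a subject with another unsolicited AE would still be counted. All analyses are descriptive (SAP section 7), and every AE remains in the by-subject listings.

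**What to change.** Add to SAP 11.2:

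> If the known part of an incomplete AE start date includes the vaccination date, the start is imputed no earlier than the vaccination date, unless the recorded (not imputed) part of the stop date shows that the AE ended before vaccination, or the AE is documented in the database as present before injection. This also applies to ongoing AEs and to AEs with an incomplete stop date. An imputed stop date may not precede the start date; if it does, it is set to the start date.

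Also state in SAP 6.5.2.3 whether the imputed start date sets the vaccine-emergent flag.

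This wording was checked over 32 cases: 2 types of partial start (day missing, year only) × (3 types of stop date × 5 durations + 1 with no stop date). No post-vaccination AE was dated before vaccination, and no stop preceded its start.

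**Cost.** A few lines of SAP text and programming. The exception for AEs present before injection needs that information in the database. No passage says it is there, and Protocol 7.1 places pre-vaccination AEs in the source document; if it is absent, those AEs need a data query.

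The trade-off is over-counting. For AEs with a missing start day and onset in the 21 days before vaccination, with no pre-injection documentation, the share counted as emergent changes as follows:

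| Stop date | Current rule | With floor |
|---|---|---|
| Complete, 14 days after onset | 36% | 50% |
| Complete, 28 days after onset | 8% | 64% |
| Day missing | 0% | 64% |

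For a safety table, over-counting is the conventional direction in which to err, but it is a choice and the SAP should state it.

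### SAP 11.2 dates most incomplete stop dates to the earliest possible day, which can record medication still in use after vaccination as already stopped

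*SAP*

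**What the plan says.** SAP 11.2 gives four rules for an incomplete stop date when the start date is complete:

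- Day missing, stop in the start month: "when the month and year are identical to a complete start date then the stop date is imputed to the start date".
- Day missing, stop in another month: "then the stop day is imputed to the first day of the month".
- Day and month missing, stop in the start year: "when the year is identical to a complete start date then the stop date is imputed to the start date".
- Day and month missing, stop in another year: "when the year is not identical to a complete start date then the start day/month is imputed to 31dec".

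No rule compares the imputed stop with the vaccination date, the last contact date or an entry of ongoing.

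SAP 6.5.2.6 tabulates by vaccine group the subjects "starting/reporting concomitant medications during all study period". It does not define concomitant use or say what part dates play. Protocol 6.5 (Version 2) has a Prior and Concomitant Medications eCRF, which takes relevant medication from the four weeks before study start. It treats as concomitant anything taken at or after enrolment.

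For adverse events, SAP 6.5.2.3 says: "Solicited adverse events continuing beyond day 7 will be coded by MedDRA and combined with the respective unsolicited adverse events". Protocol 7.1.1 has the site enter such a reaction on the Adverse Event CRF.

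**The concern.** The rules disagree in direction. Three give the shortest duration that the record allows, and the fourth gives the longest. Among year-only stops, the imputed date swings from the start date to 31 December according to whether the start fell in the same year. No reason is given. The fourth rule also sets the start day and month although its premise is a complete start date, so a literal program would overwrite a known start.

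For a medication record, an early stop is the unsafe direction. The useful question is whether a subject was taking a drug around or after vaccination. A rule that can only shorten duration can move a drug that spanned vaccination into the prior category and out of the concomitant table.

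**Working it through.** **Inputs.** The missing-day rules come from SAP 11.2. The following are assumptions: 2017 as the calendar year, every vaccination date equally likely, true stops spread evenly over the days after vaccination, medication begun before vaccination, stop month known, stop day missing.

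**When is such a medication dated as over before vaccination?** Let V be the day of the month of vaccination, L the length of that month and s the days from vaccination to the true stop.

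- Stop in a later month than vaccination: the imputed stop is the 1st of that later month, which falls after vaccination. No error.
- Stop in the vaccination month, start in an earlier month: the imputed stop is the 1st, which precedes vaccination unless V = 1.
- Stop in the vaccination month, start in that month too: the imputed stop is the start date, which precedes vaccination. Here V is at least 2.

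So the error occurs exactly when V ≥ 2 and V + s ≤ L. It does not depend on how long before vaccination the drug was begun. Each month contributes L − 1 − s vaccination days (zero if negative). Over the 12 months of 2017 this is 365 − 12 − 12s = 353 − 12s for s up to 27. At s = 28, February drops out and the count is 18; at s = 29 it is 7; from s = 30 it is 0.

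**Results.** Each denominator is 365 × the number of stop days.

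| True stop within | Misdated combinations | Total | Share |
|---|---|---|---|
| 7 days | 7 × 353 − 12 × 28 = 2,135 | 2,555 | 84% |
| 14 days | 14 × 353 − 12 × 105 = 3,682 | 5,110 | 72% |
| 28 days | 27 × 353 − 12 × 378 + 18 = 5,013 | 10,220 | 49% |
| 84 days | 5,013 + 7 = 5,020 | 30,660 | 16% |

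A direct enumeration of all dates gives the same counts.

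**Example.** A drug begun on 20 February and stopped on 25 March, with vaccination on 10 March and the stop recorded only as March, is imputed to stop on 1 March. That is nine days before vaccination.

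**Enrolment as the cut.** Protocol 6.5 uses enrolment, which may precede vaccination. If enrolment is e days earlier and the drug was begun before it, each month contributes L − 1 − s − e days (zero if negative). For true stops within 7 days of vaccination the share is then about 61% (e = 7), 38% (e = 14) or 15% (e = 21), against 84% at e = 0.

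**Medication begun on or after vaccination.** The imputed stop is never earlier than the start, so none is dated as over before vaccination (0 of 1,334,075 date combinations).

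**Last-day rule.** The last day of the true stop month is never before the true stop, so the error falls to 0%. The opposite error appears. A drug that truly stopped s days before vaccination is carried to vaccination or later whenever both dates share a month, which is 365 − 12s vaccination days. For true stops 1–7, 1–14 and 1–28 days before vaccination this is 2,219/2,555 = 87%, 3,850/5,110 = 75% and 5,348/10,220 = 52%.

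**The case against.** The strongest objection is that no planned table is defined by a stop date. SAP 6.5.2.6 counts subjects starting or reporting medication, and the site may already classify use on the eCRF. The table also counts subjects, so someone with another drug begun after vaccination is counted anyway. This stands as a limit: an effect on the table requires that concomitant status be derived from imputed dates, which the SAP neither states nor excludes. In addition, this is one site with up to 50 subjects, interviewed at Days 8, 15, 29 and 85, so partial dates may be few.

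A reader might infer more, namely that reactions lasting past Day 7 would be dated as over and the adverse event profile would look better. At the level of dates the effect exists. With onset on Days 1–7, a true stop on Days 8–28 and only the stop day missing, about 64% of imputed stops fall on or before Day 7. The documents do not carry this into a count:

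- Continuation past Day 7 is captured by entry on the Adverse Event CRF (Protocol 7.1.1).
- The unsolicited analysis takes events by CRF record and start date (Protocol 8.4.2.1.3), and SAP 6.5.2.3 summarises by onset.
- The reaction still counts in the solicited tables by maximum severity (SAP 6.5.2.2).
- The combined table ignores the duration of solicited events (SAP 6.5.2.4).

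Nor does every incomplete stop go to the earliest day, because the different-year rule goes to the latest.

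**Conclusion.** The stop-date rules are inconsistent in direction, and one line names the wrong date. Both are visible in the text and need no assumption. The practical consequence is mainly for concomitant medication: drugs spanning vaccination with only the stop day missing would often be dated as prior, in 84% of cases for stops within 7 days, falling to 16% for stops within 84 days.

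These shares are conditional on a partial date, on even timing, on vaccination as the cut and on a date-based classification. They are not estimates of how many subjects would be misclassified, since the documents give no frequency of partial dates. An earlier enrolment cut lowers them, the more so the earlier enrolment is. No change in planned adverse event counts is shown. For a descriptive Phase 1 trial this is a minor point, worth correcting because the correction is cheap.

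**What to change.** In SAP 11.2, use one principle in all four branches. Impute a stop with a missing day to the last day of the stated month, and a year-only stop to 31 December of the stated year. Cap both at the subject's last contact date and never place the stop before the start. In the last line, replace start with stop. In SAP 6.5.2.6, say whether the cut is enrolment or vaccination and whether status comes from the eCRF or from dates. In SAP 6.5.2.3, state that entry on the Adverse Event CRF, not an imputed date, decides whether a solicited reaction continued beyond Day 7.

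The cost is a few lines of SAP text and one derivation program. The downside is that some durations are overstated and some prior medication with a partial stop date is counted as concomitant, at the conditional rates shown above. For a safety description that is the more cautious error.

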12. ANNEX 2: SUMMARY ON ELIMINATION CODES

Table 12-1 Safety Sets

| PD code | PD Description | Study Period | All Exposed Set | Overall Safety Set | Safety Set, Unsolicited AEs, All study period | Safety Set, Solicited AEs, Period T30-D7 |
|----------------|---|---------------------|------------------------|---------------------------|--|---|
| | Exclusion code | | EXPFL | SAFL | SSU10FL | SSS10FL |
| 100 | Study vaccine not administered AT ALL | All Study | EXC | EXC | EXC | EXC |
| 115 | Subject did not provide any post-vaccination unsolicited safety data | All Study | | | EXC | |
| 116 | Subject did not provide any post-vaccination solicited safety data | All Study | | | | EXC |

EXC = excluded from this analysis set.

Table 12-2 Immunogenicity Sets

| PD code | PD Description | Study Objective/Period | All Exposed | FAS (Overall) |
|----------------|--|-------------------------------|--------------------|----------------------|
| | Exclusion code | | EXPFL | FAS_0 |
| 100 | Study vaccine not administered AT ALL | All Study | EXC | EXC |
| 110 | Serological results are not available (all time points) | All Study | | EXC |

FAS = Full Analysis Set;

